## Background

Stroke is the most common cause of acquired disability in adulthood (Krishnamurthi et al., 2020). After a stroke, every third survivor develops depression, and every fourth survivor develops an anxiety disorder, significantly affecting rehabilitation and quality of life (Blöchl et al., 2019; Kim et al., 2018; Liu et al., 2023; Rafsten et al., 2018). The most commonly studied psychotherapeutic approach after a stroke is cognitive-behavioral therapy (CBT), but the evidence for this approach's efficacy is heterogeneous (Allida et al., 2023; Gao et al., 2016; Lincoln & Flannaghan, 2003). This may be attributed to inadequate adaptation to language and cognitive impairments and a limited fit of the CBT approach for stroke survivors (Kneebone, 2016; Robinson et al., 2019).

An alternative to CBT is a modern, mindfulness-based development of behavioral therapy: Acceptance and Commitment Therapy (ACT). ACT principles are conveyed through metaphors, visualizations, and behavioral exercises. This approach does not directly aim to reduce psychopathology like depressive symptoms but aims to improve psychological flexibility, which is understood as a central resource of mental health. Pilot studies suggest the effectiveness of ACT in individuals with brain damage (Majumdar & Morris, 2019; Rauwenhoff et al., 2023; Sathananthan et al., 2022).

Group therapies are also suitable after a stroke, as they are both economically feasible and implementable in neurological rehabilitation facilities. Additionally, the diversity of perspectives and social integration can promote mental health (Ladwig et al., 2023; McCracken & Gutiérrez-Martínez, 2011).

The efficacy of ACT group therapy has not been investigated after a stroke up to now, and there is no German-language manual adapted for the treatment of individuals with brain injury. Therefore, this pilot study examines the feasibility, acceptance, and preliminary efficacy of an adapted ACT group therapy manual, developed in the UK and proven efficacious in treating individuals with brain damage (e.g., stroke, traumatic brain injury, and brain tumor surgeries) (Bowers et al., 2021).

The manual was translated into German and adjusted to the needs of stroke survivors, who often have a higher age, more comorbidities, and specific neurological impairments compared to the general group of brain-damaged individuals. To reduce cognitive load and adapt to conventions in the German healthcare system, the session duration is shortened from 165 minutes to 90 minutes. Additionally, the study tests outcome questionnaires translated into German and/or simple language for the first time to adjust them to the participants' cognitive capacity.

## Objectives

The study aims to provide answers to the following research questions

1. Is the group therapy program feasible?
2. Is the group therapy program accepted by stroke survivors and therapists?
3. Are there first indications on the efficacy of the group therapy to improve psychopathology and/or ACT-specific outcome measures?

Feasibility is hereby assessed via quantitative and objective indicators in accordance with a previous study investigating the efficacy of ACT in people with acquired brain damage (Sathananthan et al., 2022). These indicators include recruitment rates ( $\geq 3$  participants per group within six months), drop-out rates  $\leq 20\%$ , group attendance  $\geq 80\%$  (out of 8 participants \* 8 sessions = 64), homework completion rates  $\geq 50\%$  (for each session from participants present in session), completion rates of outcome measures  $\geq 80\%$ , treatment fidelity  $\geq 80\%$  (adherence to objectives and contents listed in the manual). Fidelity ratings are based on video recordings of two randomly selected sessions. A research assistant rates the therapists' behavior according to a checklist developed for that session.

Patients rate therapy acceptance with a validated "group therapy session questionnaire" (GTS-P; Zoubek, 2013), which includes six items for each session assessing for example active involvement and comprehensibility of contents, and two items for the entire group therapy on satisfaction and prospect of success. Therapists rate therapy acceptance with a co-developed questionnaire (GTS-T) including twelve items for each session which assess the same six contents as the patients' questionnaire and additional six items on the therapist's involvement and satisfaction. Therapists also rate acceptance for the entire group therapy for each patient on six items also resembling the six items of the patient session questionnaire (GTS-TP). All items are rated on a five-point Likert scale (0 = not true at all to 4 = absolutely true). Mean ratings in a previous study investigating a group therapy for people with diabetes and depression ranged from 2.26 to 2.86 in the different versions of the questionnaire (Zoubek, 2013). Accordingly, a mean value higher than 2 is considered as adequate therapy acceptance by patients and therapists in this study.

Preliminary efficacy is evaluated both via reducing of psychopathological symptoms and increasing of ACT-specific outcomes. ACT aims to improve psychological flexibility, which itself consists of the six processes present in the moment, acceptance, cognitive defusion, self-as-context, values and committed action (Hayes, 2016). In addition to the overall construct of psychological flexibility, the subconstructs valued living and self-as-context are investigated in this study. Valued living represents the action-focused component of *commitment* in ACT and was also reported to increase in people participating in the original group therapy program (Bowers et al., 2021). Self-as-context represents an ACT-specific conceptualization of the self. Self-concept was repeatedly demonstrated as an important determinant of mental health after brain injury (Ownsworth, 2014), yet self-as-context represents the so far least often investigated subconstruct of psychological flexibility in ACT research (Foote et al., 2023). Hence, we included these processes in this pilot study for the investigation of preliminary efficacy.

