## Study Design

The study employs a pre-post design without a control group. Consequently, there is no randomization or blinding to conditions. Group therapy is conducted with two groups, each consisting of six individuals. The therapy consists of 8 sessions, each lasting 90 minutes. A 30-minute diagnostic examination with questionnaires, including socio-demographic and health-related data, current psychopathology (depressive symptoms, PHQ-9; Kroenke et al., 2001; psychological burden, DASS-21; Lovibond & Lovibond, 1995; anxiety, GAD-7; Spitzer et al., 2006), and ACT-specific outcomes (valued living, VQ; Smout et al., 2014; psychological flexibility, AAQ-ABI; Sylvester, 2011; self-as-context, SACS; Zettle et al., 2018) takes place just before the first session. AAQ-ABI and SACS were translated into German for the first time according to recommendations using independent forward and backward translations (Wild et al., 2005). The questionnaires PHQ-9, DASS-21, GAD-7, AAQ-ABI, VQ, and SACS were also translated into plain language by a professional translation service ("Office for Easy Language Bethel", Bielefeld). After each session, participants and therapists rate the session using the GTS-P and the GTS-T, respectively. After the last session, all participants answer the same questionnaires as before the first session. They evaluate the entire therapy in the GTS-P and indicate if they would recommend the therapy to a friend with similar complaints (yes/no). The pre- and post-assessments are conducted by a trained assistant to exclude biases from the study therapists as facilitators. After the last session, therapists rate the entire therapy for each patient using the GTS-TP.

In a session form, therapists also record the participation of individual persons (Yes/No) and the completion of homework assignments (Yes/No/Incomplete) for each session. If not completed or incomplete, subjective obstacles are queried and documented. This serves to examine feasibility regarding session adherence and homework completion (objective 1).

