## Selection and Exclusion of Subjects

The participants are recruited through initial consultations at the university's neuropsychological outpatient clinic as well as through self-help groups and practitioners in the region involved in the aftercare of stroke survivors. For this purpose, information flyers are sent to neurological rehabilitation clinics as well as neurological, physiotherapy, occupational therapy, and speech therapy practices. Information and contact details for the study are also published on the homepage of the outpatient clinic and the research unit. Eligibility is evaluated by the principal investigator in an a-priori screening session using relative's information as additional source, if possible.

The study includes N = 12 adult individuals who:

1. have experienced a stroke (ischemic infarction or intracerebral hemorrhage);
2. report increased distress according to the DASS-21;
3. demonstrate sufficient cognitive and linguistic abilities; and
4. show sufficient motivation for therapy.

Increased distress according to the DASS-21 is defined as exceeding a cutoff on at least one of the three subscales of the questionnaire (Depression = D > 10, Anxiety = A > 6, and Stress = S > 10; Nilges & Essau, 2015). In the initial consultation, the cognitive and linguistic performance is assessed based on the participants' self-report and, if applicable, that of a family member, supplemented by the external judgment of the study leader, who has extensive experience in clinical work with individuals with brain damage. If the participant, possibly with input from a family member, and the study leader agree that the person can effectively participate in and benefit from 90-minute group therapy sessions on a weekly basis, the criterion is considered fulfilled. Finally, therapy motivation is assessed by participants assuring their willingness to change their approach to the illness, attend sessions regularly, and complete homework assignments within the therapy program as fully as possible.

Exclusion criteria are assessed based on self-report and external reports by the interested individual, the study leader, and possibly a family member, and include:

1. Interaction or behavioral disorders that significantly hinder group participation (e.g., significantly increased irritability or apathy);
2. Other severe psychiatric disorders (dementia, psychosis, personality disorder, intellectual disability); and

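### The attendance criterion fixes 64 possible attendances, but groups of six allow only 48, so judged per group the 80% mark cannot be reached even at full attendance

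*Combined protocol and SAP*

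**What the plan says.** The Objectives section lists six quantitative feasibility indicators for research question 1. Attendance must reach 80%, and the possible attendances are given as "out of 8 participants \* 8 sessions = 64".

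The design is described differently elsewhere:

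- Study Design: "Group therapy is conducted with two groups, each consisting of six individuals", and "The therapy consists of 8 sessions, each lasting 90 minutes".
- Selection and Exclusion of Subjects: "The study includes N = 12 adult individuals who" meet the listed criteria. This agrees with two groups of six.

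Three further statements bear on the point. In the same sentence of the Objectives, the recruitment indicator asks for at least three "participants per group within six months". That sentence also limits the homework indicator, "for each session from participants present in session"; attendance carries no such limit. The Statistical Analysis Plan judges feasibility against the cut-offs in the Objectives and gives no other denominator.

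**The concern.** The session count agrees across sections, but the participant count does not. Eight participants matches neither one planned group (6) nor the whole sample (12), so 64 is not the number of possible attendances in any unit the plan describes.

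Because the figure sits inside a predefined threshold, it can change the reported verdict. The direction depends on something the plan leaves open: whether attendance is judged for each group or over both. Per group is more natural, since the indicator is called group attendance and recruitment in the same sentence is counted per group. On that reading the criterion is too strict for the planned design to pass. On the pooled reading it is too lenient.

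Attendance is one of the six indicators that answer the first research question, and the Study Design section says the session form is kept for that purpose. If the line stays as it is, the analyst must either apply a threshold that does not fit the design or choose a denominator once the data are in, which defeats the purpose of fixing the criterion in advance.

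**Working it through.** **Inputs.** Threshold 80% and denominator 8 × 8 = 64 (Objectives); 8 sessions and two groups of 6 (Study Design); N = 12 (Selection and Exclusion of Subjects); recruitment minimum of 3 per group (Objectives).

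**Formulas.** Possible attendances = participants × sessions. Attendances needed = 0.80 × denominator, rounded up.

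**The plan's figure.** 8 × 8 = 64 is correct as a product. From the design, the count is 6 × 8 = 48 per group or 12 × 8 = 96 overall. Neither is 64.

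**Threshold as printed.** 0.80 × 64 = 51.2, so 52 attendances. Since 52 / 8 = 6.5, a group needs at least 7 members to reach it.

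**Per-group reading.** Highest possible score when nobody misses a session:

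| Group size | Attendances | Score out of 64 |
|---|---|---|
| 3 (recruitment minimum) | 24 | 37.5% |
| 4 | 32 | 50.0% |
| 5 | 40 | 62.5% |
| 6 (planned) | 48 | 75.0% |
| 7 | 56 | 87.5% |

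Every size from the recruitment minimum to the planned six fails at full attendance. For six members the correct requirement is 0.80 × 48 = 38.4, so 39 attendances. Results of 39 to 48 out of 48 (39/48 = 81.3%, up to 100%) are therefore wrongly failed. At 38/48 = 79.2% or below, failing is the right answer.

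**Pooled reading, N = 12.** The printed rule passes from 52/96 = 54.2%. The correct requirement is 0.80 × 96 = 76.8, so 77 attendances (77/96 = 80.2%). Results of 52 to 76 out of 96 (54.2% to 79.2%) are therefore wrongly passed. Full attendance would score 96/64 = 150%.

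**The case against.** The best defence is that the cut-off is the percentage and the bracket is only a stale worked example. Participation is recorded for each person and session, so the real denominator will be visible at analysis. Used literally, 64 would give 75% for a group with perfect attendance, or as much as 150% pooled, and either result would probably be noticed. This stands to a degree: a wrong report is a possible outcome, not a certain one. But nothing in the text marks the 64 as an illustration, and the Statistical Analysis Plan points back to that line without offering another figure. If an example was intended, the line still needs rewording.

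A second objection is that three per group is a minimum for calling recruitment feasible, whereas the design fixes groups at six, so the ceilings for three to five members describe unplanned cases. It is true that they follow from the same wrong figure and that the case for six is sufficient alone. They still show that a group of three could satisfy the recruitment indicator while being unable to satisfy the attendance indicator beside it.

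Finally, the plan does not say how drop-outs count towards attendance. Keeping them in the denominator is an inference from the contrast with the homework indicator, so the sponsor needs to confirm it.

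**Conclusion.** The inconsistency is real and should be corrected. The printed denominator fits neither 48 nor 96. Applied literally per group, the planned design cannot pass, and a group of six with true attendance of 81.3% to 100% is reported as failing. Applied literally to both groups together, true attendance of 54.2% to 79.2% is reported as passing.

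These results assume that 64 is used as written, that groups are filled to six (12 in total for the pooled case), and that all eight sessions take place. The per-group reading is more natural but not stated. Because the group size and the sample size agree with each other, eight participants looks like the odd figure; its origin is not given, and only the sponsor can say which number is current.

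The consequence is limited. No stop/go rule depends on this indicator, the true percentage can be recovered, and the other five feasibility indicators and the acceptance, efficacy and safety analyses are unaffected.

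**What to change.** Reconcile the attendance line in the Objectives with the Study Design and selection sections.

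- If two groups of six is current, replace the fixed 64 with the number of participants enrolled in the group × 8 sessions. As planned, that is 48 possible attendances per group with at least 39 required. If the verdict is taken over both groups, it is 96 with at least 77 required.
- If eight per group is current, correct the other two sections instead. With two groups retained, N becomes 2 × 8 = 16.
- State, before attendance is tabulated, whether the verdict is per group or pooled.
- State in the same line how drop-outs count. The wording above keeps them in the denominator; if the sponsor intends otherwise, it should say so there.

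The cost is one line of protocol and SAP text (plus the group and sample sizes if eight per group is current). No new data are needed, because participation is already recorded by person and session.

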## Study Design

The study employs a pre-post design without a control group. Consequently, there is no randomization or blinding to conditions. Group therapy is conducted with two groups, each consisting of six individuals. The therapy consists of 8 sessions, each lasting 90 minutes. A 30-minute diagnostic examination with questionnaires, including socio-demographic and health-related data, current psychopathology (depressive symptoms, PHQ-9; Kroenke et al., 2001; psychological burden, DASS-21; Lovibond & Lovibond, 1995; anxiety, GAD-7; Spitzer et al., 2006), and ACT-specific outcomes (valued living, VQ; Smout et al., 2014; psychological flexibility, AAQ-ABI; Sylvester, 2011; self-as-context, SACS; Zettle et al., 2018) takes place just before the first session. AAQ-ABI and SACS were translated into German for the first time according to recommendations using independent forward and backward translations (Wild et al., 2005). The questionnaires PHQ-9, DASS-21, GAD-7, AAQ-ABI, VQ, and SACS were also translated into plain language by a professional translation service ("Office for Easy Language Bethel", Bielefeld). After each session, participants and therapists rate the session using the GTS-P and the GTS-T, respectively. After the last session, all participants answer the same questionnaires as before the first session. They evaluate the entire therapy in the GTS-P and indicate if they would recommend the therapy to a friend with similar complaints (yes/no). The pre- and post-assessments are conducted by a trained assistant to exclude biases from the study therapists as facilitators. After the last session, therapists rate the entire therapy for each patient using the GTS-TP.

In a session form, therapists also record the participation of individual persons (Yes/No) and the completion of homework assignments (Yes/No/Incomplete) for each session. If not completed or incomplete, subjective obstacles are queried and documented. This serves to examine feasibility regarding session adherence and homework completion (objective 1).

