## Statistical Analysis Plan

Missing values are replaced by multiple imputation including all assessed variables. Outliers are identified by visual inspection and inclusion/exclusion is decided on a case-by-case approach. Estimates are calculated based on 95% confidence intervals.

Feasibility (research question 1) is assessed by frequencies fulfilling the predefined cut-offs (see objectives).

The acceptance score of  $> 2$  is evaluated by Wilcoxon-tests for one sample (one-sided) for all versions of the GTS (-P mean of single sessions and entire therapy, -T, and -TP). Significant changes in primary outcomes psychological flexibility (AAQ-ABI) and psychological burden (DASS-21) are assessed with Wilcoxon-tests for paired samples (one-sided);  $p$ -value is Bonferroni-adjusted ( $p = .025$ ). Significant changes in secondary outcomes valued living (VQ), self-as-context (SACS), depressive symptoms (PHQ-9), and anxiety symptoms (GAD-7) are assessed with Wilcoxon-tests for paired samples (one-sided);  $p$ -value is Bonferroni-adjusted ( $p = .0125$ ). Individual changes in primary and secondary outcomes are also based on reliable change indices with a significance level of  $\alpha = .90$  (one-sided).

Sensitivity analyses examine the influence of the baseline variables age, gender, kind of stroke (ischemia vs. hemorrhage), current use of prescribed psychotropic drugs (yes/no), previous mental disorder (yes/no), and previous use of psychotherapy (yes/no) on changes in primary and secondary outcomes. These bivariate associations are investigated by Pearson correlations (for continuous covariates) and Chi tests (for categorical covariates;  $p = .05$ , two-sided) using the difference scores of the outcomes. Likewise, associations between therapy acceptance and the changes in efficacy outcomes (AAQ-ABI, DASS-21, VQ, SACS, PHQ-9 and GAD-7) are exploratively analyzed.

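### Acceptance ratings have no route for people who leave, and missing ones are multiply imputed with no not-at-random check, so the mean > 2 test can be biased upward if people leave from dislike.

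*Combined protocol and SAP*

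**What the plan says.** Under Study Design, acceptance is collected at two kinds of time point. The first is the session: "After each session, participants and therapists rate the session using the GTS-P and the GTS-T, respectively". The second is the post-assessment: "After the last session, all participants answer the same questionnaires as before the first session", and at that visit "They evaluate the entire therapy in the GTS-P and indicate if they would recommend the therapy to a friend with similar complaints". Therapists add their own view of each patient: "After the last session, therapists rate the entire therapy for each patient using the GTS-TP". No exit rating is described, and no recording of why a participant left. The obstacles that therapists document concern homework.

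Under Objectives, "a mean value higher than 2 is considered as adequate therapy acceptance by patients and therapists in this study". Drop-out (at most 20%), attendance (at least 80%) and completion of outcome measures (at least 80%) are separate feasibility indicators and do not enter this criterion.

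Under Statistical Analysis Plan, the acceptance score "is evaluated by Wilcoxon-tests for one sample (one-sided) for all versions of the GTS", covering both the mean of the single sessions and the entire therapy. The whole missing-data rule is: "Missing values are replaced by multiple imputation including all assessed variables". It does not exempt acceptance ratings, and no sensitivity analysis addresses ratings that are missing because of dislike.

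**The concern.** For most outcomes, drop-out is a nuisance loosely related to the value that goes missing. For an acceptance rating, leaving may itself express low acceptance. Standard multiple imputation assumes that, given the observed data, a leaver would have rated as a comparable stayer did. If some people leave because they dislike the therapy, that assumption errs in the therapy's favour.

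At stake is the patient half of research question 2. It could be answered yes on ratings given by, or borrowed from, those who stayed. With 12 participants, two missing ratings are a sixth of the data.

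**Working it through.** The plan gives no power or expected result for the acceptance test, so there is no figure to reproduce. The check asks how far missing leavers could move the result, and how much of that imputation would recover.

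**Inputs from the documents.** N = 12 ("The study includes N = 12 adult individuals who"); scale 0 to 4; criterion mean > 2; one-sided one-sample Wilcoxon test; drop-out at most 20%; mean ratings of 2.26 to 2.86 in the earlier group-therapy study cited under Objectives. The 20% limit tolerates 2 leavers (2/12 = 16.7%; 3/12 = 25%).

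**Assumptions.** Leaver ratings as shown; alpha .05, since none is stated for this test; untied ranks.

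**1. Mean over all enrolled** = [(12 − d) × stayer mean + d × leaver rating] / 12, with d = 2.

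- Stayers 2.26, leavers 0: 22.6/12 = 1.88. Leavers 1: 24.6/12 = 2.05.
- Stayers 2.86, leavers 0: 28.6/12 = 2.38. Leavers 1: 30.6/12 = 2.55.
- Stayer mean needed for an all-12 mean of exactly 2: 24/10 = 2.40 (leavers 0) or 22/10 = 2.20 (leavers 1).

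**2. Exact signed-rank test, worst case.** Suppose all stayers score above 2 and the leavers have the largest deviations below 2.

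- Ten stayers alone: W− = 0, p = 1/2^10 = 0.001.
- All 12, two leavers: W− = 12 + 11 = 23, p = 0.117.
- All 12, one leaver: W− = 12, p = 0.017, still significant.

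**3. Chance of a significant result, completers only (n = 10) against all 12 observed.** Simulated with SD 0.6. This is not the planned imputation; it marks the end of the range where imputation recovers nothing.

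| Stayer mean | Leaver mean | Completers | All 12 |
|---|---|---|---|
| 2.3 | 1.0 to 1.5 | 38% | 5 to 17% |
| 2.5 | 1.0 to 1.5 | about 74% | 18 to 42% |
| 2.5 | 2.0 | about 74% | 67 to 68% |
| 2.86 | 1.0 to 1.5 | 99% | 61 to 87% |

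**4. What imputation recovers.** Illustrative regression imputation of the whole-therapy rating (4,000 runs): 2 of 12 leave, true leaver rating about 0.5, stayer mean 2.5, SD 0.7. The predictor is the leaver's own earlier session rating. The last column is (10 × 2.5 + 2 × imputed value)/12; the true value is (25 + 1)/12 = 2.17.

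| Correlation of earlier with whole-therapy rating | Imputed leaver mean | All-12 mean |
|---|---|---|
| no predictor | 2.50 | 2.50 |
| 0.3 | 2.32 | 2.47 |
| 0.5 | 2.01 | 2.42 |
| 0.7 | 1.53 | 2.34 |
| 0.9 | 0.89 | 2.23 |

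Under these assumptions the imputed value is too high in every row, by less as the earlier rating becomes more predictive. A model with all assessed variables is also hard to fit here. The patient questionnaire alone gives 6 × 8 = 48 session items plus 2 whole-therapy items for 12 people, so some reduction or shrinkage is unavoidable, and that may push imputed values toward the average.

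**The case against.** A reader might infer that leavers are simply counted as average accepters. The documents do not support that. Imputation is to use all assessed variables, which include a leaver's own session ratings and the GTS-TP if given. Someone who leaves after session 3 may have three ratings of their own, and the session mean is tested as an acceptance score in its own right. The average-accepter result holds only where no predictive rating exists.

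A reader might also infer that the whole-therapy rating is restricted to completers. No sentence says so: the post-assessment is set for all participants. The gap is silence on how leavers are reached.

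Nor is the direction of bias known. The Background describes stroke survivors as often older and with more comorbidities, so illness is a plausible reason for leaving that has nothing to do with dislike. With leavers at 2.0, the simulated gap nearly closes.

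Finally, heavy leaving is not hidden: three leavers of 12 already fail the drop-out criterion.

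These arguments narrow the point but do not remove it. An instruction covering all participants, without a procedure for those who have left, does not produce their ratings, and the SAP itself expects missing values. Flagging drop-out elsewhere leaves the acceptance mean and its test unchanged. Without recorded reasons, nobody can tell afterwards whether illness or dislike explains the missing ratings.

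**Conclusion.** The point holds in a conditional form. The plan has no stated route to ratings or reasons from people who leave, and no not-at-random check on imputed acceptance. If people leave from dislike, the mean > 2 test is biased upward, most strongly when leavers gave no informative earlier rating.

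Within the plan's own drop-out limit this can decide the result but need not. With two leavers at 0, the low end of the cited range falls from 2.26 to 1.88 and fails, while the high end falls from 2.86 to 2.38 and passes. With leavers at 1, both pass on the mean. In the worst-case pattern the Wilcoxon p moves from 0.001 to 0.117.

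These sizes rest on assumed leaver ratings and alpha .05, and the simulated percentages also on SD 0.6. The percentages compare completers with full observation, so they are not the bias of the planned imputation. This should be changed, but it does not undermine the pilot as a whole.

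**What to change.** 1. Offer the whole-therapy GTS-P and the recommendation question when a participant leaves, and record the reason for leaving. The plan already has therapists telephone people who miss a session without notice, though for safety, so contact of this kind is practicable.
2. Report observed acceptance ratings with the number of raters, per session and for the whole therapy. Do not rest the acceptance conclusion on ratings imputed as missing at random for drop-outs.
3. Add, labelled as a worst-case sensitivity analysis, the proportion of all enrolled participants rating above 2, with unrated drop-outs counted as not accepting and an exact 95% CI. For example, 10/12 = 83%, CI 52 to 98%. It should not be the main result: it treats withdrawal for illness as dislike, and at n = 12 the interval is wide.

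The cost is one short form for about two people and one extra line of analysis. The downside is a possibly less favourable acceptance figure.
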